Rhee et al reviewed 24 studies of ED thoracotomies in the literature with 4,620 cases. Presumably this is a group of patients who had become pulseless in the ED and the clinicians felt that there was some hope for successful resuscitation. The overall survival, however, was only 7%, with >90% of survivors having normal neurologic outcomes. Several factors seemed to influence survival rates: 1) penetrating (9% survival) was better than blunt (1%) trauma mechanisms, and stab wounds (17%) were better than gunshot wounds (4%); 2) thoracic injuries (11%) were better than abdominal (5%) or multiple (1%); 3) signs of life on arrival at the hospital (12%) vs no signs of life (3%), and signs of life in the field (9%) vs no signs of life (1%). Based upon this type of data, Hall and Buchman have developed a timeline for decision-making in patients who have suffered a cardiac arrest from trauma based on mechanism of injury, vital signs and signs of life. Recognizing the frequent futility of resuscitative efforts in patients who have suffered a cardiac arrest from trauma, the National Association of EMS Physicians and the American College of Surgeons Committee on Trauma have published guidelines for withholding or terminating resuscitation in these patients. Though intentionally left up to local protocols, they did recommend termination of resuscitation after 15 min unsuccessful CPR or, once cardiac arrest has occurred, if >15 min is required for transport. These data have lead trauma specialists to seek novel approaches to management of trauma victims who suffer cardiac arrest.

In 1984, Colonel Ronald Bellamy, a U.S. Army surgeon, and [name] reviewed military casualty data. The majority of soldiers killed in action in Vietnam without brain trauma had penetrating truncal injuries [4]. They exsanguinated internally over a few minutes. Such casualties are still considered unresuscitable though many have technically repairable injuries upon autopsy. Bellamy and Safar agreed that a novel approach was necessary, i.e., Emergency Preservation and Resuscitation (EPR).

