The goal will be to enroll 10 subjects that undergo EPR and 10 concurrent control subjects. A detailed report will be filed with the FDA after the first 5 subjects in each group have been discharged or have expired. A final report will be filed after the hospital courses of 10 subjects in each group have been completed. All interim and outcome reports from the DSMB will also be sent to the USAMRMC ORP HRPO.

Outcome data and data analysis

Survival to hospital discharge without major disability, MODS scores, survival at 28 days, GOSE and SF-36 (at 6 and 12 months) will be compared between groups. Complications felt to be possibly or definitely associated with of the EPR technique will be specifically recorded. As with any cardiac arrest resuscitation trial, there is a risk that a subject will survive with a poor neurologic outcome (e.g., comatose, vegetative). Based on the current literature for survivors of cardiac arrest from trauma with standard card, this risk is small.

The decision to proceed with further clinical investigation of the EPR technique will depend upon the frequency of associated complications (in relation to the high risk of death and morbidity secondary to the original injuries) and lack of inferiority to standard care with regard to the secondary endpoints. Based on information learned during the course of the study, the entry criteria may be revised in order to select subjects most likely to benefit from the intervention. The technique for EPR may also be revised. Evaluating these new criteria or techniques may justify further investigation. If, despite revisions of entry criteria and technique, survival appears to be no better than (or worse than) standard care, the study could be stopped. The FDA, ORP HRPO, and reviewing IRBs will be notified of such revisions prior to their implementation.

VIII. INCLUSION / EXCLUSION CRITERIA

Inclusion criteria

Subjects must meet all of the following inclusion criteria:

- Penetrating trauma with clinical suspicion of exsanguinating hemorrhage
- Age 18-65
- At least 1 sign of life at the scene (pulse, respiratory efforts, spontaneous movements, reactive pupils)
- Loss of pulse <5 min prior to ED arrival or in the ED or operating room
- Thoracotomy performed without immediate return of a palpable pulse in the carotid arteries after clamping the descending thoracic aorta

Exclusion criteria.

Subjects will be excluded for any of the following:

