The decision to enroll subjects into this trial will have to be made promptly by the trauma team resuscitating the subject. Information available to them will include the mechanism of injury, time from injury and paramedic arrival to ED arrival, physical examination for signs of life (pulse, breathing, spontaneous movements, reactive pupils), cardiac rhythm, and response to standard resuscitative efforts. This information will be available from Medic Command and the paramedics who transport the subject. Since time is of the essence, little more information may be available. The most important information for screening will be the condition of the subject upon arrival in the ED or operating room and the response to the standard resuscitative efforts, i.e., with either no or only transient restoration of pulse. No other screening procedures will be performed.

The number of subjects in this initial feasibility trial will be 20 (10 EPR and 10 concurrent control). After review of these subjects by the investigators, DSMB, FDA, and ORP-HRPO, a decision will be made to either discontinue the study, proceed with another cohort of subjects with revised inclusion criteria or EPR technique, or consider a randomized, pivotal trial.

X. INFORMED CONSENT PROCESS

This clinical study qualifies for the "Exception from informed consent for emergency research" outlined in the FDA regulation at 21 CFR Section 50.24. Listed below are the respective regulatory criteria and corresponding justifications for the applicability of this clinical study.

(1) The human subjects are in a life-threatening situation, available treatments are unproven or unsatisfactory, and the collection of valid scientific evidence, which may include evidence obtained through randomized placebo-controlled investigations, is necessary to determine the safety and effectiveness of particular interventions.

These potential subjects are clearly in a life-threatening situation with unsatisfactory available treatments, as evidenced by a <10% chance of survival based on current literature. The collection of valid scientific evidence is necessary to determine the safety and effectiveness of EPR.

- (2) Obtaining informed consent is not feasible because:
 - (i) The subjects will not be able to give their informed consent as a result of their medical condition;
 - (ii) The intervention under investigation must be administered before consent from the subjects' legally authorized representatives is feasible; and

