Title 10 United States Code 980 states that "Funds appropriated to the Department of Defense may not be used for research involving a human being as an experimental subject unless- (1) the informed consent of the subject is obtained in advance; or (2) in the case of research intended to be beneficial to the subject, the informed consent may be obtained from a legal representative of the subject."

Even though there is intent to benefit patients enrolled in this study, the informed consent of the LAR is likely not going to be possible to secure in advanced, hence a waiver of 10 USC 980 will be requested.

XI. DATA COLLECTION, ANALYSIS and COORDINATION

Data collection

Procedures to assess efficacy:

The primary outcome variable will be survival to hospital discharge without major disability (Glasgow Outcome Scale-Extended >5) after resuscitation with EPR in exsanguinating trauma patients, compared to concurrent or historic control patients. the ability (feasibility) and safety of inducing EPR. Secondary outcomes will include: 1) the feasibility and safety of rapidly inducing profound cerebral hypothermia for EPR in exsanguinating trauma patients, 2) 28-day survival, 3) 6 and 12-month neurologic functional outcome (Glasgow Outcome Score Extended [GOSE]) and SF-36, and 4) the development of multiple organ dysfunction syndrome (MODS) (see Table: Multiple Organ Dysfunction Score) in the EPR group, as compared to a concurrent control group and historical controls.

Once the EPR subject has been rewarmed and, if possible, weaned from CPB, there will be no additional invasive procedures performed on the subject for the specific purpose of the research study. The subject will continue to undergo standard medical procedures as indicated for the clinical care of his/her trauma injury.

For subjects in both arms of the study, the medical record will be utilized to determine the occurrence of multiple organ system dysfunction or death.

The MODS Score (Table) will be utilized to quantify the level of organ system dysfunction.

Neurologic functional outcome will be assessed in survivors using the GOSE and SF-36 at 6 and 12 months. If the subject is discharged from the hospital prior to either of these dates, GOSE information will be obtain via telephone calls to the subject or the subject's LAR.

			Score		
Organ system	0	1	2	3	4
Respiratory (PO ₂ /FiO ₂)	>300	226-300	151-225	76-150	< 75

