Renal (serum creatinine - µmol/l)	< 1.1	1.2-2.3	2.4-3.9	4.0-5.6	>5.7
Hepatic (serum bilirubin - µmol/l)	< 1.1	1.2-3.5	3.6-7.1	7.2-14.1	>14.2
Cardiovascular (PAR*)	< 10.0	10.1-15.0	15.1-20.0	20.1-30.0	>30.0
Hematologic (platelet count –x 10 ⁻³)	>120	81-120	51-80	21-50	< 20
Neurologic (Glasgow coma score)	15	13-14	10-12	7-9	< 6

The GOSE is defined as:

- 1. Dead
- Vegetative state
- 3. Lower severe disability
- 4. Upper severe disability

- 5. Lower moderate disability
- 6. Upper moderate disability
- 7. Lower good recovery
- 8. Upper good recovery

Procedures to assess safety:

The safety of the EPR procedures will be continually monitored during the subject's hospitalization. Although complications specifically associated with the EPR procedures will likely be difficult to differentiate from complications arising from the subject's trauma and/or standard resuscitative efforts, we will attempt to do so. These could include, but are not limited to, injuries to vascular structures, air or clot embolism, and hemolysis. Hypothermia can lead to coagulopathy.

Induction of EPR in a pulseless trauma victim bears the risk of survival with significant neurologic dysfunction after restoring circulation in a patient who would otherwise have expired. As this outcome is possible with standard care also, this will be difficult to assess, but will be monitored in relation to the concurrent control group.

Outcome data and data analysis.

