The primary outcome measure is survival to hospital discharge without major disability (Glasgow Outcome Scale-Extended ≥5). Secondary outcomes include survival at 28 days, GOSE and SF-36 (at 6 and 12 months) will be compared between groups. Complications felt to be possibly or definitely associated with the EPR technique will be specifically recorded. The decision to proceed with further clinical investigation of the EPR technique will depend upon the frequency of associated complications (in relation to the high risk of death and morbidity secondary to the original injuries) and lack of inferiority to standard care with regard to the secondary endpoints. Based on information learned during the course of the study, the entry criteria may be revised in order to select subjects most likely to benefit from the intervention. The technique for EPR may also be revised. Evaluating these new criteria or techniques may justify further investigation. The FDA, ORP HRPO, and reviewing IRBs will be notified of such revisions prior to their implementation.

Data Coordination

Data will be collected at each site on the attached case report form (Appendix C). The information will be transmitted via a secure website to the data collection center at the University of Pittsburgh. Each subject will be assigned a unique code for the study. No patient identifiers will be transmitted to the data center. Links to personal identifiers will be maintained in locked filing cabinets at each site.

XII. LABELING & STORAGE OF DATA & SPECIMENS

A Case Report Form (CRF, see Appendix B) will be completed for each subject (both arms) enrolled into the clinical study. The responsible investigator for each study site will review, approve and sign/date each completed CRF; the investigator's signature serving as attestation of the investigator's responsibility for ensuring that all clinical and laboratory data entered on the CRF are complete, accurate and authentic.

The CRF will be electronically transmitted to the data center at the University of Pittsburgh without patient identifiers.

The investigator-sponsor and study site investigators will maintain records in accordance with Good Clinical Practice guidelines to include:

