Anticipated risks of the EPR procedure itself include, but are not limited to, injuries to the vascular structures that are cannulated (aorta, femoral vessels, right atrium), air or clot embolism, and hemolysis. These risks will be minimized by extensive additional training of involved, experienced surgical and critical care personnel and the use of FDA-approved cannulae and equipment. Hypothermia carries the risk of coagulopathy. Aggressive replacement of clotting factors and platelets during rewarming will help minimize this risk.

In addition, as in any resuscitation trial, there is a risk of resuscitating a subject who would otherwise have died, but survives with significant neurologic deficits. This is complicated by the fact that some survivors of cardiac arrest from trauma also survive with neurologic deficits. The comparative risks are unknown. The risk of long-term survival with severe neurologic dysfunction will be minimized by consideration, with involvement of the subject's LAR, for withdrawal of care when the predicted chance for meaningful neurologic recovery is very low.

The expected mortality for the potential subjects to be included in this study, when treated with the current standard of care, is >90%. Based upon preclinical studies as described in the Background section above (section VII), EPR has the potential to improve outcome of these subjects. Thus, the benefit-to-risk ratio is favorable.

XIV. BENEFIT(S)

Potential subjects are clearly in a life-threatening situation with <10% chance of survival with currently available treatments. Animal studies suggest that EPR may improve chances for survival in these patients, thus there is potential for direct benefit. Given the high mortality in this situation, the relative risk of EPR is reasonable.

XV. COMPENSATION

There is no compensation for participation in this study. Emergency medical treatment for injuries solely and directly related to participation in this research study will be provided by the hospital. It is possible that hospital may bill insurance providers for the costs of this emergency treatment, but none of these costs will be charged directly to the subject. If any research-related injury requires medical care beyond this emergency treatment, the subject may be responsible for the costs of this follow-up care unless otherwise specifically stated. There is no plan for monetary compensation

XVI. CONFIDENTIALITY

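### Six- and 12-month GOSE and SF-36 are assessed in survivors and then compared between groups, so EPR can look inferior when it rescues patients who recover less well than the few control survivors

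*Protocol*

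**What the plan says.** Section XI (Data collection, Procedures to assess efficacy) sets who is assessed: "Neurologic functional outcome will be assessed in survivors using the GOSE and SF-36 at 6 and 12 months".

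Section VII (Outcome data and data analysis) sets the use: "MODS scores, survival at 28 days, GOSE and SF-36 (at 6 and 12 months) will be compared between groups". The section of the same name in XI repeats it: "Secondary outcomes include survival at 28 days, GOSE and SF-36 (at 6 and 12 months) will be compared between groups". Both sections then make the decision to proceed depend on the frequency of complications and on "lack of inferiority to standard care with regard to the secondary endpoints".

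The GOSE levels listed in sections VII and XI start with Dead as level 1. No sentence says that a subject who has died is scored 1 in the 6- or 12-month comparison. The protocol gives no value for death on the SF-36.

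**The concern.** EPR is meant to raise survival. A functional comparison restricted to the living therefore selects subjects on an effect of treatment, and the two sets of survivors need not be alike.

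The protocol supplies the ingredients for a distorted result. Section XIII expects mortality above 90% under current care, so control survivors will be few. The literature review in section VII (Rationale) suggests that they will also be in good condition: "The overall survival, however, was only 7%, with >90% of survivors having normal neurologic outcomes". For EPR, section XI (Procedures to assess safety) says that induction "bears the risk of survival with significant neurologic dysfunction after restoring circulation in a patient who would otherwise have expired". Each such patient lowers the average among EPR survivors, while the comparable control patient has died and is not counted.

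At stake is one of the conditions for going on: a technique that leaves more patients alive and well could appear inferior on long-term function.

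**Working it through.** **Plan's own figure.** There is none to reproduce. The protocol states no margin, effect size or calculation for this comparison. The check asks what the stated procedure would give.

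**Inputs from the protocol.**
- 10 EPR subjects and 10 concurrent controls, not randomised (section IX).
- Standard-care survival of 7% in the literature review (section VII), and below 10% expected in this trial (section XIII).
- More than 90% of survivors neurologically normal in that review. I take 0.90 as the chance of a good outcome for a patient who would survive under either treatment.

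**Assumptions not in the protocol.** EPR survival *e* is 20% to 40%. The chance *f* of a good outcome in a patient alive only because of EPR is 0.3 to 0.9. Control survival *c* is 7% or 10% in steps 2 and 3.

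**Step 1: number of control survivors out of 10.** P(none) = (1 − *c*)^10. P(at most one) = (1 − *c*)^10 + 10·*c*·(1 − *c*)^9.

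| Control survival | P(none) | P(at most one) |
|---|---|---|
| 5% | 0.60 | 0.91 |
| 7% | 0.48 | 0.85 |
| 9% | 0.39 | 0.78 |
| 10% | 0.35 | 0.74 |

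At 7%: 0.93^10 = 0.484, and 0.484 + 10 × 0.07 × 0.93^9 = 0.848.

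**Step 2: expected proportion with a good outcome.** Among survivors it is 0.90 in controls and [0.90·*c* + (*e* − *c*)·*f*]/*e* with EPR. Among all enrolled it is 0.90·*c* and 0.90·*c* + (*e* − *c*)·*f*.

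For *c* = 10%, *e* = 30%, *f* = 0.5, the EPR figure in all enrolled is 0.09 + 0.20 × 0.5 = 0.19, against 0.09 in controls. Among survivors it is 0.19/0.30 = 0.63, against 0.90. The order reverses.

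For *c* = 7% and *e* = 30%:

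| *f* | Survivors: EPR (control 90%) | All enrolled: EPR (control 6.3%) |
|---|---|---|
| 0.9 | 90% | 27.0% |
| 0.7 | 75% | 22.4% |
| 0.5 | 59% | 17.8% |
| 0.3 | 44% | 13.2% |

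**Step 3: chance that EPR looks worse in a trial of this size.** This is a simulation with 200,000 replicates and 10 per group, counting trials with at least one survivor in each group. For *c* = 7% and *e* = 30%, the proportion good among survivors is lower with EPR with probability 0.50, 0.67 and 0.78 for *f* = 0.7, 0.5 and 0.3. Counting all enrolled in the same trials gives 0.12, 0.20 and 0.31. For *c* = 10%, *e* = 30%, *f* = 0.5 the probability falls from 0.63 to 0.22. Over every combination tried, the survivor-based probability runs from 0.18 to 0.85.

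**Step 4: two illustrations with invented scores.** In both, one control is alive at GOSE 7 and nine have died.
- EPR survivors at 3, 4 and 6, with seven deaths. Survivor means are 13/3 = 4.3 v 7.0. With deaths at 1, means are (13 + 7)/10 = 2.0 v (7 + 9)/10 = 1.6. Of the 100 EPR–control pairs, EPR wins 27, ties 63 and loses 10. The win probability with ties counted as half is 0.27 + 0.315 = 0.585.
- EPR survivors at 7, 6, 5 and 3, with six deaths. Survivor means are 21/4 = 5.25 v 7.0. With deaths at 1, they are 27/10 = 2.7 v 1.6. Two EPR subjects against one control are above GOSE 5, so EPR looks worse among survivors although more of its patients are alive with good function.

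**The case against.** The strongest reply is that the survivor sentence concerns data collection. Only the living can be interviewed, and the next sentence covers telephone follow-up. The listed GOSE includes Dead, the case report form in Appendix B records vital status beside GOSE, and the comparison is worded as between groups. A statistical analysis plan could score deaths as 1. This stands in part: a reader might infer that deaths are certainly left out of the GOSE comparison, and the documents do not say so. They leave it open on an endpoint that enters a decision. The reply does not help the SF-36.

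A reader might infer that the decision to proceed rests on this comparison alone. It does not. Complications and 28-day survival also enter, section VII lets the study stop if survival appears no better than standard care, and section IX leaves the decision to review by several bodies. The final FDA report follows completion of the hospital courses, so the 6- and 12-month data may not be complete by then.

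A reader might extend the point to MODS. The protocol takes MODS from the medical record for both arms and does not restrict it to survivors.

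Historical controls, at least 10 eligible, could add survivors. Section XI names them for the secondary outcomes, while the secondary objective in section VII names concurrent controls only. Pooling 20 controls at 7% still gives P(none) = 0.93^20 = 0.23, and more survivors do not remove the selection.

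Finally, having no control survivor is a small-sample limit. It leaves the comparison undefined and does not make EPR look inferior.

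**Conclusion.** The point holds as a cheap improvement. As written, the long-term functional comparison conditions on survival. It is firm for the SF-36 and ambiguous for the GOSE. The primary outcome and 28-day survival count deaths and are unaffected.

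The distortion is conditional. It would go too far to say that the comparison is always biased against an effective treatment: if rescued patients recover as well as control survivors (*f* = 0.9), the expected proportions are equal. The reversal needs rescued patients to do worse, which the protocol names as a risk but does not quantify. EPR survival and *f* are my assumptions, so the probabilities in step 3 show a range and are not predictions.

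The control-survivor counts need only the assumed survival rate. At 7%, the comparison has no control survivor in about half of such trials and at most one in 85%.

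**What to change.** In section VII (Outcome data and data analysis) and section XI (Procedures to assess efficacy; Outcome data and data analysis), state that:
- GOSE at 6 and 12 months is compared in all enrolled subjects, with deaths scored 1, as an ordinal (rank) comparison;
- the GOSE distribution among survivors is also shown descriptively, so that impaired survival stays visible;
- SF-36 is reported descriptively in survivors beside the number alive in each group, and is outside the lack-of-inferiority condition.

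The cost is a change of wording. Appendix B already records vital status and GOSE at long-term follow-up. One small downside is that, with mortality this high, the all-enrolled GOSE comparison will largely track survival, which is why the survivor distribution should stand beside it.

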Once hemostasis has been achieved, CPB will be initiated (if low flow CPB had not been continued throughout) for reperfusion and slow rewarming. The goal will be to keep the total time of circulatory arrest under 1 hour and to minimize the duration of low flow at profound hypothermia. The rewarming rate will be targeted at 0.5°C/min. During rewarming, transfusions of standard (i.e., for clinical use) packed red blood cells, fresh frozen plasma, cryoprecipitate, and platelets will be administered to achieve a hemoglobin of at least 8 gm/dl, normalized prothrombin time (INR <1.5) and activated partial thromboplastin time (PTT), fibrinogen level of 150 mg/dl, and platelet count of >100,000. Thromboelastograms may also be followed. Activated clotting times (ACT) will be monitored. If hemostasis is acceptable, the ACT will be maintained at >180 sec with intravenous heparin as needed until CPB is discontinued.

Rewarming will continue until Tty reaches 34°C. Mild hypothermia (Tty 34°C) may be maintained for 12 h to optimize neurologic recovery using external cooling plus sedation and paralysis as needed. If coagulopathy persists despite aggressive correction with blood products (to platelet count of 100,000 and normal PT/PTT and fibrinogen), rewarming to normothermia may be considered. More prolonged post-resuscitation hypothermia may be considered in selected subjects with poor neurologic function at 12 hours with no contraindication to mild hypothermia.

Shivering will be treated with sedation (propofol), analgesia (fentanyl), and, if necessary, neuromuscular blockade.

Decannulation should be performed as soon as the subject has sufficiently stable spontaneous circulation to be weaned from CPB. The thoracotomy should then be closed. If the subject requires more prolonged circulatory support, the use of Extracorporeal Life Support (ECLS) via extrathoracic (usually femoral or jugular) cannulation can be considered. ECLS may be appropriate for a subject who can not be weaned from CPB because of hypotension (despite inotropes/vasopressors or an intra-aortic balloon pump) or inadequate oxygenation (e.g., PaO2 to FiO2 ratio consistently less than 100), yet otherwise seems to have potential for long-term survival.

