Thoracotomy tray and standard trauma resuscitation equipment and supplies will be available per standard care of trauma patients. Specific equipment for this study that will be readily available in the ED will include: large volumes of ice-cold saline in a refrigerator (30 liters stored in a designated refrigerator for this trial), arterial and venous cannulae (various sizes and types), appropriate tubing, CPB pump, and hollow-fiber membrane oxygenator/heat exchangers. This equipment will be stored in a storage area near the trauma resuscitation rooms in the Emergency Department. It will be labeled at the site with the following warning: "CAUTION -Investigational Device/Drug. Limited by Federal (or United States) law to investigational use."

Concurrent Control Group:

We will collect data on concurrent patients who are appropriate candidates for EPR, but do not have EPR initiated because the team is not available. These data will include specifics of resuscitative efforts and the same outcome parameters as the EPR group. Per the request of the FDA, 10 concurrent control subjects will be entered and a detailed report will be submitted to the FDA prior to any further subject enrollment.

Historical Control Group:

Because of concern that bias may influence the selection of subjects who receive EPR, thus affecting the concurrent control group, outcome information regarding similar patients in the trauma registry of the respective institutions (Level I trauma centers) will be obtained. The most recent 100 patients who had undergone an ED thoracotomy will be reviewed. Additional subjects may be required in order to obtain at least 10 subjects who would have met criteria for entry into the study.

Consent:

Due to the emergency nature of the traumatic event and the need for immediate resuscitation, including initiation of EPR, this study must be performed under the Exception from Informed Consent for emergency research as outlined in FDA regulation 21CFR50.24. Once the subject has been stabilized, consent for continued participation in the study for collection of data and long-term follow-up, will be obtained from the subject's legal authorized representative (LAR). In addition, consent for follow up will be obtained for survivors in the control group. (See section X below for additional information regarding the exception from consent conditions, request, and justification.)

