Appendix B: Case Report Form

OVERVIEW OF SUBJECT DATA

EPR ID	
DATE OF INJURY	
HOSPITAL	
AGE	
ETHNICITY	
GENDER	
MECHANISM OF INJURY	
TIME PULSE LOST	
TIME EPR DECISION	
OBVIOUS NON SURVIVABLE	
EVIDENCE OF TBI	
ASYSTOLE	
MASSIVE TRAUMA	
PREGNANCY	
PRISONER	
TRANSPORTATION TYPE	
AGENCY NAME	
VEHICLE #	
TIME 911 CALL	
TIME ARRIVAL AT SCENE	
TIME DEPARTING SCENE	
TIME ED ARRIVAL	

ED Resuscit	ation Summary	Daily	Followup
WORST SBP		WORST SBP	
WORST DBP		WORST DBP	
WORST HR		WORST HR	
WORST RR		WORST RR	
BEST GCS		BEST GCS	
CRYSTALLOIDS		CRYSTALLOIDS	
COLLOIDS		COLLOIDS	
PRBC		PRBC	
FFP		FFP	
PLATELETS		PLATELETS	
CRYO		CRYO	
НВ		НВ	
WBC		WBC	
PT		РТ	
PTT		PTT	
PLT COUNT		PLT COUNT	
PAO2		PAO2	
SAO2		SAO2	
FIO2		FIO2	
VENTILATOR RATE		VENTILATOR RATE	
VENTILATOR TV		VENTILATOR TV	
CREAT		CREAT	
BILIRUBIN		BILIRUBIN	

ED Thoracotomy EPR ID OPERATION TITLE OP DATE TIME START TIME CROSS CLAMP AORTA TIME UNCLAMP AORTA TIME AORTIC CANNULA PLACED TIME FLUSH STARTED TIME GOAL TEMP REACHED TIME FLUSH COMPLETED STERNUM TRANSECTED? **BLOOD LOSS FROM STERNUM** EBL OP CRYSTALLOIDS OP COLLOIDS OP PRBC OP UO TIME CBP STARTED TIME CBP STOPPED **OPERATIONS** EPR ID **OPERATION TITLE** EBL OP DATE OP CRYSTALLOIDS **OP COLLOIDS** OP PRBC OP UO

	INJURIES		
	EPR ID		
INJURY I	REGION		
ABBREVIATED INJURY SEVERITY			
(COMPLICATION		
EPR ID			
COMPLICATION			
INFE EPR ID INFECTION DATE OF ONSET	CTION COMPLICATIONS		
	ONG TERM FOLLOW UP		
ALIVE			
GOSE			
RESPONDENT			

MANUFACTURER INFORMATION

IRB#	Principal Investigator:
Event date:	Date event reported to PI:
Subject ID:	Protocol: Same Different
Event report: Initial Follow-up #	Enrollment site: XXXXX
Research Drug/Device/Intervention: Brief Description of Event:	
Action Taken:	
Causality: Definite Possible (there is a reasonable possibility that the adverse event, incident, experience or outcome may have been caused by the procedures involved	Event Severity: Serious (meets one of the following criteria) A modification should be considered. >Death >Life threatening (places subject at immediate risk
in the research) Unrelated	of death from the event as it occurred) >Results in inpatient hospitalization or prolongation of existing hospitalization >Results in a persistent or significant
Probability: Expected	disability/incapacity >Results in a congenital anomaly/birth defect >Based upon appropriate medical judgment, may

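### The MODS table labels creatinine and bilirubin in µmol/l, but its cut-offs work only in mg/dl

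*Protocol*

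**What the plan says.** The MODS scoring table appears twice in the Protocol: in Section VII under Outcome, and in Section XI under the procedures to assess efficacy. The row headings agree: "Renal (serum creatinine - µmol/l") and "Hepatic (serum bilirubin - µmol/l"). The cut-offs also agree:

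| Item | 0 | 1 | 2 | 3 | 4 |
|---|---|---|---|---|---|
| Creatinine | ≤1.1 | 1.2–2.3 | 2.4–3.9 | 4.0–5.6 | >5.7 |
| Bilirubin | ≤1.1 | 1.2–3.5 | 3.6–7.1 | 7.2–14.1 | >14.2 |

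The table is operative. Section XI states: "The MODS Score (Table) will be utilized to quantify the level of organ system dysfunction". The data-analysis paragraph of Section VII lists it among the comparisons: "MODS scores, survival at 28 days, GOSE and SF-36 (at 6 and 12 months) will be compared between groups".

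No other place gives a different unit for these two analytes. In Appendix B the creatinine and bilirubin fields carry no unit. Where the Clinical protocol section sets laboratory targets, it uses conventional units, for example "fibrinogen level of 150 mg/dl" and hemoglobin in gm/dl.

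**The concern.** Label and cut-offs cannot both be right. If the label is followed, the renal item becomes a constant and the hepatic item reaches its maximum within normal values. Two of the six items in the Section XI copy then lose most or all of their power to separate well from badly functioning organs.

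There are two different consequences:

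- **Label followed throughout.** Both groups shift upward alike, so no false group difference arises. A true difference in renal function would be invisible, however, and one in hepatic function largely so. Both data-analysis paragraphs let the decision to proceed rest partly on EPR being no worse than standard care on the secondary endpoints, and a score that cannot discriminate makes groups look alike.
- **Label followed for some records only.** Identical organ function then receives different scores. Historical controls rely on "outcome information regarding similar patients in the trauma registry of the respective institutions", and nothing fixes the unit of those values.

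**Working it through.** **Inputs from the Protocol.** The row labels and cut-offs tabulated above, identical in Sections VII and XI. The maximum score is 6 items × 4 = 24, using the six-row copy in Section XI.

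**Inputs assumed (not in the Protocol).** Conversion factors from molar mass: creatinine 88.4 and bilirubin 17.1 µmol/l per mg/dl. Normal ranges: creatinine up to 1.1 mg/dl; bilirubin 0.3–1.2 mg/dl, with 0.1 mg/dl tried as an alternative lower limit.

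**Step 1: read the label literally and convert the cut-offs to mg/dl** (cut-off ÷ factor).

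- Creatinine 1.1 / 2.3 / 3.9 / 5.6 / 5.7 µmol/l = 0.012 / 0.026 / 0.044 / 0.063 / 0.064 mg/dl.
- Bilirubin 1.1 / 3.5 / 7.1 / 14.1 / 14.2 µmol/l = 0.064 / 0.205 / 0.415 / 0.825 / 0.830 mg/dl.

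Even a creatinine of 0.1 mg/dl is 0.1 × 88.4 = 8.8 µmol/l, above 5.7, so it scores 4. No plausible patient scores anything else on the renal item.

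**Step 2: score bilirubin values under both readings.**

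| Bilirubin, mg/dl | µmol/l | Score as labelled | Score in mg/dl |
|---|---|---|---|
| 0.1 | 1.7 | 1 | 0 |
| 0.3 | 5.1 | 2 | 0 |
| 0.5 | 8.6 | 3 | 0 |
| 0.7 | 12.0 | 3 | 0 |
| 0.9 | 15.4 | 4 | 0 |
| 1.2 | 20.5 | 4 | 1 |

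**Step 3: two-item total for a patient with normal kidneys and liver.**

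- As labelled: 4 + 2 = 6 up to 4 + 4 = 8 (4 + 1 = 5 at a bilirubin of 0.1 mg/dl).
- In mg/dl: 0 + 0 = 0, or 0 + 1 = 1 at a bilirubin of 1.2 mg/dl.

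**Step 4: loss of discrimination.**

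| Creatinine, bilirubin (mg/dl) | Total as labelled | Total in mg/dl |
|---|---|---|
| 1.0, 1.0 | 4 + 4 = 8 | 0 + 0 = 0 |
| 6.0, 15 | 4 + 4 = 8 | 4 + 4 = 8 |

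An 8-point difference in organ function disappears.

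**Step 5: mixed handling.** A patient with creatinine 1.0 and bilirubin 0.7 mg/dl scores 4 + 3 = 7 if the values are converted to µmol/l, and 0 if they are entered in mg/dl.

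**Step 6: does mg/dl work?** Yes. Creatinine of 1.0, 2, 3, 4.5 and 6 mg/dl scores 0, 1, 2, 3 and 4. Bilirubin of 1.0, 3, 8 and 15 mg/dl scores 0, 1, 3 and 4. Both rows then grade from normal to severe.

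**The case against.** The strongest reply is that the slip reveals itself and would probably do no harm. The two active sites are in Baltimore and Pittsburgh, the Protocol's laboratory targets are in gm/dl and mg/dl, and anyone applying the label literally would soon notice every renal score at 4. The case report form shown collects raw creatinine and bilirubin with no field for a MODS score, and the forms go to one data center. That is consistent with a single central derivation, so mixed scoring is conjecture. No laboratory field on the form carries a unit, so the gap is not peculiar to these two.

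The role of MODS is also uneven in the text. The secondary objective compares it with concurrent controls only, and the Section XI data-analysis paragraph leaves it off the list of secondary outcomes. With 10 EPR and 10 concurrent control subjects, and expected mortality above 90% under standard care, few control subjects may yield informative values.

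Much of this stands as a limit on weight. Mixed units are a possibility, not something the Protocol shows will happen, and the points per subject do not translate into a known effect on the decision. None of it makes the table correct. The Protocol does not say who derives the score or in which unit, and later rescoring from raw values needs a known unit, which the form does not record. An extraction fault is unlikely, because the same label stands in two rows of two separate copies with identical cut-offs.

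**Conclusion.** The concern holds: as printed, the renal and hepatic rows carry the wrong unit for their cut-offs. Following the label fixes the renal item at 4 for any creatinine above 0.064 mg/dl, and gives the maximum hepatic score for any bilirubin above 0.83 mg/dl. The cost is 6 to 8 spurious points out of 24 for a patient with normal organs, where the intended score is 0 or 1.

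The conversion factors and normal ranges are assumptions, but the conclusion hardly depends on them. The renal result needs only that patients' creatinine exceeds 0.064 mg/dl, and the hepatic one only that the upper normal limit of bilirubin exceeds 0.83 mg/dl.

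The consequences are limited to a secondary outcome and arise only where the label is followed. Scoring directly in mg/dl gives the intended result. The error should be corrected, but it does not threaten the primary comparison.

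**What to change.** Change the unit in the renal and hepatic rows to mg/dl in both copies of the table. Print that unit beside the creatinine and bilirubin fields in Appendix B, and record the unit of every value taken from the trauma registries for historical controls.

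If µmol/l is preferred, convert the cut-offs instead: upper limits of about 97 / 203 / 345 / 495 for creatinine (1.1, 2.3, 3.9, 5.6 × 88.4) and 19 / 60 / 121 / 241 for bilirubin (1.1, 3.5, 7.1, 14.1 × 17.1). A rounding rule is then needed: a creatinine of 1.1 mg/dl is 97.24 µmol/l and would slip from score 0 to score 1 against a limit of 97. Relabelling is simpler.

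While editing, check whether the top bands should read ≥5.7 and ≥14.2. As they appear, values of exactly 5.7 and 14.2 belong to no band, though this may only be an underline lost when the PDF was read.

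The cost is two row labels in each of two tables, two form fields, and a unit noted for registry values. Neither the design nor the measurements collected change.
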